Impact on patient care. One of the factors that contributes to second ACL injury is incomplete or ineffective rehabilitation.⁵⁴ Aberrant neuromuscular and biomechanical patterns are commonly seen up to 2 years after ACLR and may help explain the high rate of second ACL injury.¹¹⁻¹⁶ Deficits in the neuromuscular control of both lower extremities following ACLR have been directly implicated in the risk for second ACL injury¹⁵ and may not only be a result of the initial knee injury and subsequent surgery, but may also characterize the athlete's pre-injury movement patterns. Therefore, identification and subsequent targeted treatment of

aberrant post-ACLR movement patterns for both limbs are critical not only to maximize functional recovery but also to reduce the risk for second ACL injury. Though neuromuscular training programs result in a 73.4% decreased risk of a non-contact primary-ACL injury compared to those who do not participate in neuromuscular training⁵⁵, the efficacy of similar programs for reduction of second-ACL injury risk has not been examined.

An evidence-based targeted neuromuscular training (TNMT) program has been designed to reduce the incidence of second ACL injury. This training program was developed with consideration to modifiable factors related to second-injury risk, the principles of motor learning, and careful selection of the exercises that may most effectively modify aberrant neuromuscular programs. In Aims 2 and 3 of this competing renewal proposal we will evaluate the effects of differential treatment interventions. Notably, we will assess the effectiveness of TNMT, including the utilization of visual and verbal biofeedback. Validation of this evidence-based, late-phase TNMT program may significantly impact clinical practice patterns through its integration in rehabilitation settings, and serve as a critical factor in reduction of second injury risk. Ultimately, determining if less intensive HOME and STAN training programs are effective interventions for patients who are at reduced risk for second ACL injury may prove to be a tremendous time and cost savings for patients and the health-care system.

Study Design and Methods

Methods

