where (i) K is the number of mixture components (groups), (ii) π_k is the unconditional probability that a subject fall into the k th group, and (iii) $\phi(\cdot; \mu, \Sigma)$ is the multivariate normal density with mean μ and covariance Σ . Estimates of the parameters, π_k, μ_k, Σ_k , are typically obtained using maximum likelihood. The number of groups is most commonly chosen to optimize the Bayesian Information Criterion (BIC). Often assumptions such as a common covariance matrix for all k , or common shape (i.e., correlation) matrix, are made to make estimation feasible, depending on the size of data, and these decisions are also commonly made on the basis of BIC. In this work we intend to assume a common Σ , and assess the validity of this assumption via model diagnostics. Once parameter estimates are obtained, clustering is performed by calculating the probability of group membership m for a given subject, conditional on his/her covariate values, i.e.,

$$P(m = k | x) = \frac{\pi_k \phi(x; \mu_k, \Sigma_k)}{\sum_{l=1}^K \pi_l \phi(x; \mu_l, \Sigma_l)}.$$

The subject will then be assigned to the group k that results in the largest conditional group membership probability $P(m = k | x)$. This approach has been shown to perform very well in the presence of a large number of variables with the inclusion of a variable selection mechanism.^{71, 72} We will leverage such an approach in our analysis to identify a reduced set of biomechanical variables that most informatively differentiate the subjects.

Aim 2:

Aim 2 will utilize a prospective, single blind, randomized clinical trial design. Subjects from Aim 1 will comprise the study sample. Subjects will undergo testing twice.

We will use a repeated-measures ANOVA model with between-subjects factors that include interactions, to determine the effect of TNMT compared to HOME or STAN treatment on clinical performance after ACLR. Specifically, for a response of interest y , e.g., hip abductor strength, for the i^{th} subject in the k^{th} treatment group, with $l = 0$ indicating before intervention and $l = 1$ indicating after,

$$y_{ikl} = \alpha + \delta_l + (\gamma\delta)_{kl} + \tau_{i(k)} + \epsilon_{ikl}$$

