with (i) intercept α , (ii) subject random effect $\tau_{i(jk)} \sim N(0, \sigma_{\alpha}^2)$, (iii) pure error (or noise) $\epsilon_{ijk1} \sim N(0, \sigma_{\epsilon}^2)$, (iv) δ_l is the main effect due to intervention, and (vi) $(\gamma\delta)_{kl}$ is the interaction effect allowing intervention efficacy to vary with intervention type. The fixed effects are constrained such that $\delta_0 = (\gamma\delta)_{k0} = 0$. In this model, the baseline (i.e., pre-treatment) response for an individual is:

$$y_{ikl} = \alpha + \tau_{i(k)} + \epsilon_{ikl}.$$

Thus, the pre- intervention response for a given subject is the same regardless of which intervention group k they were assigned to, since nothing would have happened yet within their intervention group to distinguish them from other groups. Under the formulation in (1), the difference between observations before and after intervention is:

$$d_{ijk} = y_{ijk1} - y_{ijk0} = \delta^* + \gamma_k^* + \epsilon_{ijk}^*$$

where $\delta^* = \delta_1$, $\gamma_k^* = (\gamma\delta)_{k1}$, and $\epsilon_{ijk}^* = (\epsilon_{ijk1} - \epsilon_{ijk0}) \sim N(0, 2\sigma_{\epsilon}^2)$. The primary inference of interest is with respect to the relative efficacy of rehabilitation type γ_k^* and the effect of risk group on intervention efficacy, along with their interaction $(\beta\gamma)_{jk}^*$. Thus, this inference could equivalently be conducted using the pairwise differences in a straightforward one-way ANOVA model. We will assess model assumptions (e.g., normality and constant variance) via residual diagnostics and apply transformations if needed. Where appropriate, we will also utilize Tukey HSD post hoc analysis to further determine significance between groups on intervention effect.

Endpoints

There will be no known direct medical benefits to subjects from participating in this study.

Primary: Completion of all study activities

Secondary: Second injury

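### Aim 2 counts the risk-group effect and its interaction with arm as primary inference, but no written model contains a risk-group term, and the one-way ANOVA offered as equivalent, read with the change equation, cannot supply one.

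*Combined protocol and SAP*

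**What the plan says.** All of this is in the Data Analysis Plan unless noted.

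- **General statement (Aim 2).** "We will use a repeated-measures ANOVA model with between-subjects factors that include interactions", with the purpose given as "to determine the effect of TNMT compared to HOME or STAN treatment on clinical performance after ACLR". Treatment is the only factor named.
- **Model.** The equation has an intercept, a time effect δ_l, an arm-by-time effect (γδ)_kl, a subject effect and error. The indices defined are i (subject), k (arm) and l (time).
- **Term list.** The list reaches (iv), where δ_l "is the main effect due to intervention, and (vi"), so there is no item (v). The subscript j appears on the subject effect and the error but is never defined.
- **Change equation.** The post-minus-pre difference d_ijk equals δ* + γ*_k + error. The j is carried as a subscript, but no effect is indexed by it.
- **Primary inference.** It covers γ*_k and "the effect of risk group on intervention efficacy, along with their interaction", written (βγ)*_jk.
- **Equivalence.** The next sentence says that "this inference could equivalently be conducted using the pairwise differences in a straightforward one-way ANOVA model".
- **Risk groups (Aim 1).** They come from mixture clustering: "The number of groups is most commonly chosen to optimize the Bayesian Information Criterion (BIC"). The plan mentions three groups in previous work but fixes no number for this trial.
- **Aims and hypotheses.** Aim 2 and Hypotheses 2A and 2B concern differences between treatment groups and do not mention risk group.

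**The concern.** A plan should let an analyst fit the model that answers its stated primary question. Here the question has three parts (arm, risk group, arm by risk group) and the written model answers one. An analyst who follows the equations reports nothing on the other two. An analyst who follows the sentence must supply a model that the plan does not contain.

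The interaction asks whether the benefit of one programme over another depends on risk group. A test by arm averages over risk groups and so misses effects that cancel across them. The Power Statement refers to the effect of TNMT and describes no risk-group or interaction test, so the size of the trial has not been checked against this part of the inference.

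**Working it through.** **1. Terms named against terms written**

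| Part of the stated primary inference | In the model? | In the change equation? |
|---|---|---|
| Arm, γ*_k | yes, (γδ)_kl | yes |
| Risk group, β*_j | no | no |
| Arm by risk group, (βγ)*_jk | no | no |

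With 3 arms and, as an assumption, 3 risk groups, the written change equation has 3 free mean parameters: an intercept and 2 arm contrasts. The full two-way layout has 3 × 3 = 9. The missing 6 are the 2 degrees of freedom for risk group and the 4 for the interaction.

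**2. The plan's own sample-size figure**

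Inputs from the Power Statement: effect size 0.17 (metric not stated; read as Cohen's f), α = 0.05, 80% power, ρ = 0.3, 87 completers. From the design: 3 arms, 2 tests. Equal arms are assumed.

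For the arm-by-time test, equivalently one-way ANOVA on change, λ = f²·N·2/(1−ρ) with df = 2 and N−3.

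- N = 87, ρ = 0.3: λ = 0.0289 × 87 × 2/0.7 = 7.18, power 65%.
- 80% power at ρ = 0.3 needs N = 120.
- N = 87 gives 80% at ρ = 0.5.

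So 87 is not reproduced from the stated inputs on this reading. That is a separate matter; the point here does not depend on it.

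**3. Power for the interaction, if it were modelled**

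Further assumptions: the same f = 0.17 applies to the interaction (the plan gives it only for TNMT), and arm-by-risk cells are equal. With J risk groups, df1 = 2(J−1), df2 = N−3J, and λ as above. At ρ = 0.3, λ is 7.18 for N = 87 and 0.0289 × 105 × 2/0.7 = 8.67 for N = 105. The 105 is 150 × 0.70, the target accrual less the stated 30% dropout (Subject Information gives 120).

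| Risk groups | 87 completers | 105 completers |
|---|---|---|
| 2 | 65% | 74% |
| 3 | 52% | 62% |
| 4 | 44% | 54% |

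With 3 groups and 87 completers, power is 69% at ρ = 0.5 and 91% at ρ = 0.7. At ρ = 0.3, 80% power with 3 groups needs 150 completers.

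**4. What a one-way ANOVA by arm sees**

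In a pure interaction with equal cells the effects sum to zero over risk groups within each arm, so the three arm means are equal. The cell differences go into the residual, which inflates the denominator and pushes rejection below 5%. Simulation with 87 completers, near-equal 3 × 3 cells, f = 0.17, three zero-sum patterns and 20,000 trials each gave rejection of about 4% at ρ = 0.3 and 3% at ρ = 0.7. The test has no power for this effect.

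**5. Where the equivalence does hold**

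With two time points, the classical arm-by-time F test is the one-way ANOVA on differences. For γ*_k alone the sentence is right under that method.

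**The case against.** The strongest reply is that this is editing residue. Aim 2, both hypotheses, the second study purpose, the Power Statement and the purpose sentence of the model all concern treatment only. Stray j subscripts and a missing item (v) are what a partly deleted factor would leave. The arm test, the only one tied to an Aim 2 hypothesis, is specified. The word primary is also local to that sentence: the Endpoints section lists completion of study activities as primary. This explanation is plausible, but it does not remove the contradiction, because the current text still claims an inference that its model lacks.

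Second, the plan does not say that the one-way ANOVA is by arm. A one-way layout over arm-by-risk cells with contrasts could carry the whole inference. That is correct, and by arm is an inference from the change equation printed just above. But no cells or contrasts are described.

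A reader might infer more than the documents support:

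- *That the trial's main value is lost.* The Background does speak of "determining if less intensive HOME and STAN training programs are effective interventions for patients who are at reduced risk for second ACL injury", but as an eventual possibility, in a paragraph that also refers to an Aim 3 absent from the current protocol. It is weak evidence of a current objective.
- *That the risk-group analysis would be chosen after seeing the data.* The plan names the parameter and describes how risk groups are formed. The terms are unwritten; an intention to choose them late is not shown.
- *That the arm analysis is wrong or biased.* Change scores match the classical arm-by-time test. Using less information than a baseline-adjusted fit does not in itself bias them.

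**Conclusion.** The point holds as an internal contradiction and is worth fixing. The stated primary inference for Aim 2 includes a risk-group effect and an interaction that no written equation contains. The analysis offered as equivalent is so for the arm effect only. This conclusion rests on the text and needs no numerical assumption. The documents do not settle whether the risk-group clause or the reduced model is the intended one.

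The power figures are conditional on reading 0.17 as Cohen's f, carrying it over to the interaction, and equal cells. On those terms, interaction power at the plan's own correlation of 0.3 is below 80% for 2 to 4 risk groups at both 87 and 105 completers. It improves with higher correlation, and the plan itself calls 0.3 likely conservative.

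**What to change.** Make the primary inference and the model agree, by one of two routes:

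- **(a)** In line with Hypotheses 2A and 2B, limit the primary inference to the arm effect. Label the arm-by-risk-group analysis exploratory and fit it as a two-way model on the change score. The cost is giving up a confirmatory answer on risk group.
- **(b)** Keep the risk-group questions primary. Write the risk-group and arm-by-risk-group terms into the model, state how the number of risk groups is fixed, and give the power. The cost is accepting low power at correlation 0.3.

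Under either route, restrict the equivalence sentence to the arm-by-time test, define or remove j, and repair the term list. These are changes of wording and small changes of code; no new patient testing is needed.

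*Separate and optional, not an error.* The arm effect could be adjusted for the pre-test, by ANCOVA or by a likelihood fit of the common-baseline model the plan writes, in which the pre-test response is "the same regardless of which intervention group k they were assigned to, since nothing would have happened yet". Change has variance 2σ²(1−ρ) and the adjusted outcome σ²(1−ρ²), a ratio of 2/(1+ρ): 1.54 at ρ = 0.3 and 1.05 at ρ = 0.9. Because the Differential Rehabilitation section sends distant patients only to HOME or STAN, such an adjustment needs a term for allocation type; in the mixed model that term must let both baseline and change differ. With the term the gain is smaller and vanishes at high correlation. Its size depends on the number of distant patients, which the documents do not give.

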Overall Strategy. This is a prospective, randomized, repeated measures single- blind clinical trial. The purposes of this study are to 1) stratify patient risk for second ACL injury, and 2) determine the effects of differential treatment intervention, including targeted neuromuscular training (TNMT), home program only (HOME) and standard clinical (STAN) training, on clinical, biomechanical, and neuromuscular performance measures associated with an increased secondary ACL injury risk. At this time there is no evidence to support one intervention as either superior or inferior to the other interventions proposed in this study. After the initial ACL injury and study enrollment, all patients will participate in standardized pre-operative rehabilitation. They will then undergo surgery by a fellowship-trained sports medicine surgeon at Mayo Clinic, Rochester, MN. Data for Aim 1 will be obtained from biomechanical, neuromuscular and clinical testing performed during Pre-Testing. Data for Aim 2 and the Exploratory Aim will be obtained from biomechanical and clinical test results obtained from Pre- and Post-Testing time points.

Common Rehabilitation. All study participants will follow the same rehabilitation guidelines before and immediately after surgery, until they are cleared by their attending surgeon to return to full participation in sports. After clearance, they will be randomized into the differential treatment groups. Entry into this phase is criteria-based, and represents the standards identified in the literature for entry into the final phase of rehabilitation. These criteria include: symmetrical knee range of motion; minimal or no pain and knee effusion; quadriceps strength $\geq 80\%$ compared to contralateral limb (180°/sec and 300°/sec); self-report of function $\geq 80\%$; limb symmetry index during single leg hop for distance $\geq 80\%$. Both pre- and postoperative rehabilitation protocols are a composite of previously published, evidence-based protocols from expert researchers and clinicians.⁶⁵⁻⁶⁷

Differential Rehabilitation. Once study participants are cleared for full participation in sports, they will be randomized into one of three groups for differential treatment. This will include HOME, STAN and TNMT

groups. If patient lives at a distance from Mayo Clinic and cannot participate in the weekly training but is able to come to both testing session they will be randomized into the HOME and STAN programs.

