Check 'None' when none of the identifiers listed above will be recorded, maintained, or shared during the conduct of this study. (exempt category 4)	 None	 None

Data Analysis

Power analyses and study endpoints are not required for minimal risk research, pilot or feasibility studies.

No statistical information. *If checked, please explain:*

Power Statement:

We expect that the minimal clinically significant effect size of TNMT on knee biomechanics is 0.17 or above. Using an a priori power analysis based on repeated measures ANOVA, we expect that to achieve 80% power with $\alpha = 0.05$, this study will require a final accrual of 87 subjects. This assumes a correlation coefficient of 0.3 among the repeated measures, which is likely conservative. Thus, an accrual of 116 (with an estimated 30% dropout rate) subjects will be sufficient to determine if a clinically significant reduction in unininvolved limb transverse plane hip net moment impulse, frontal plane knee joint ROM, initial contact sagittal plane knee moment asymmetry, and deficits of involved limb postural stability has occurred as a result of TNMT. This sample size provides adequate power for all variables of interest for Aims 1 and 2. Mayo Clinic averages more than 120 ACLR per year in the Minneapolis/Rochester region on individuals under age 25. Thus, the available patient pool is more than adequate to meet study requirements.

Data Analysis Plan:

Aim 1: We will utilize normal mixture based clustering analysis⁷⁰ to identify groups with distinguished risks based on a priori covariates (i.e., demographics and biomechanical variables). Our previous work used a similar approach to effectively cluster subjects into three distinct risk groups. We intend to confirm disparate risk for injury by assessment of the magnitude of differences across groups using knee and hip abduction angles, surrogates for ACL injury.

The normal mixture model approach works by assuming the density of the covariates for a subject x , can be described as:

$$f(x) = \sum_{k=1}^K \pi_k \phi(x; \mu_k, \Sigma_k),$$

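### Aim 2 counts a risk-group difference in raw pre-to-post change as primary inference on efficacy; for outcomes that also form the risk groups, that difference includes regression to the mean

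*Combined protocol and SAP*

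**What the plan says.** Under Data Analysis Plan, Aim 2, the response is reduced to the difference between the post- and pre-intervention values. The primary inference on that difference covers the relative efficacy of the rehabilitation types and "the effect of risk group on intervention efficacy, along with their interaction". The risk-group effect is thus listed separately from the interaction.

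The protocol defines one risk grouping, the normal-mixture clustering of Aim 1. Its timing is given under Overall Strategy: "Data for Aim 1 will be obtained from biomechanical, neuromuscular and clinical testing performed during Pre-Testing". The same patients go into Aim 2: "Subjects from Aim 1 will comprise the study sample". They are tested twice.

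The printed equations do not match that sentence. The Aim 2 model has an intercept, a time effect, an arm-by-time effect and a subject effect. The change equation has an overall shift, an arm effect and error. Neither contains a risk-group term, yet the text uses a subscript j and a beta-gamma interaction that are not defined. Hypotheses 2A and 2B compare treatment groups only.

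**The concern.** A patient's Pre value is a stable level plus session-to-session variation. Clustering on Pre values puts some patients in the high-risk group partly because that day's values were unfavourable. At Post-Testing those values tend to move back without any treatment. The change score subtracts the same Pre value that helped assign the group, so its error does not have mean zero within a risk group, although the Aim 2 derivation treats it as mean-zero noise.

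The Background section argues for directing more intensive care to patients at greatest risk. Greater improvement in the high-risk group would seem to support that, and for the overlapping outcomes some of it would be an artefact of how the groups were formed.

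**Working it through.** **1. Which outcomes are exposed.** Hypothesis 1A (grouping variables) set against Hypotheses 2A and 2B (outcomes):
- In both: frontal and transverse plane hip moments, frontal plane knee motion, quadriceps strength, single-limb balance.
- Outcome only: hip abductor and extensor strength, hop symmetry, self-reported function. These can be affected only through correlated Pre-Testing error. The plan's own worked example, hip abductor strength, is in this set.

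**2. The plan's correlation.** The Power Statement says: "This assumes a correlation coefficient of 0.3 among the repeated measures, which is likely conservative". To reproduce its sample size of 87, take the effect size of 0.17 as Cohen's f (the type is not named), three equal arms, m = 2 tests and the arm-by-time interaction, with noncentrality λ = f²·N·m/(1 − ρ).
- ρ = 0.3, N = 87: λ = 0.0289 × 174 / 0.7 = 7.18; df 2, 84; power 65%. Reaching 80% needs N = 120.
- ρ = 0.5, N = 87: λ = 0.0289 × 174 / 0.5 = 10.06; power 80.3%.

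So 87 is not reproduced at the stated 0.3 but is at 0.5. The correlation is therefore treated as a range.

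**3. Direction, in the simplest case.** With equal Pre and Post variance and no treatment effect, the expected change given Pre is −(1 − ρ) × (Pre − mean). For thirds formed on the outcome itself, the outer thirds lie 1.09 SD either side of the mean, a gap of 2.18 SD. The spurious gap in change is (1 − ρ) × 2.18:
- ρ = 0.3: 1.53 SD
- ρ = 0.7: 0.65 SD
- ρ = 0.9: 0.22 SD

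This is an extreme, because the plan clusters on several variables. With four or six variables at ρ = 0.3, simulated gaps ran from 0.28 to 0.93 SD depending on set-up. Rejection rates are therefore the more useful measure.

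**4. Null simulation.** Assumptions: no treatment effect; 87 or 105 patients; four or six measures; a common-covariance mixture forced to three groups on Pre values with modal assignment; an F test of risk group on Post minus Pre at 5%; 100 to 500 runs per setting.

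| ρ | Continuum, three groups forced | Overlapping true clusters, three groups forced |
|---|---|---|
| 0.3 | 54-59% | 50-56% |
| 0.5 | 44-47% | 28% |
| 0.7 | 28-38% | 7-27% |
| 0.9 | 12-16% | 5% |

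**5. Letting BIC choose the number of groups.**
- Continuum, six measures, 105 patients: BIC chose one group in all 150 runs at ρ = 0.3, and in 100 of 100 runs at each of 0.3, 0.7 and 0.9 in a further set.
- Clusters weak enough to keep ρ near 0.3: one group in 98% of runs.
- Clusters clearer, but BIC keeping more than one group in only 23 of 100 runs: 9% of those 23 rejected.
- Clusters distinct enough for BIC to choose three groups in 96-100% of runs: 5-10% rejected.

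**6. Alternatives to the stand-alone test.** The arm-by-risk-group interaction rejected in 3-8% of null runs throughout, about nominal. Adjusting for the outcome's own Pre value did not reliably repair the risk-group main effect: 5-21% at ρ = 0.3 and up to 40% at 0.7. Where true clusters exist, part of that reflects real differences between groups.

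**7. Power of the interaction.** Take f = 0.17, ρ = 0.3, three arms by three risk groups (4 df). Enrolling 150 with 30% dropout leaves 150 × 0.7 = 105, although Subject Information prints 120. At N = 105, λ = 0.0289 × 210 / 0.7 = 8.67 with df 4, 96, giving 62% power. Power is 52% at N = 87 and 69% at N = 120; 80% needs N = 150.

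**The case against.** Four points can fairly be made on the other side.

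- **The effect is in the sentence but not in the model.** The equations and Hypotheses 2A and 2B concern arms only, and the phrase may be left over from a fuller model. No passage states that the Aim 2 risk group is the Aim 1 cluster. This stands as a limit: the point is conditional on that reading. But the sentence declares the effect primary, and simply adding the missing term would run the affected test.
- **BIC might form no groups where the bias is largest.** This stands and reduces the size substantially. It does not remove the point, because the plan describes BIC as common practice rather than as a binding rule and cites three groups in earlier work.
- **Visits may correlate far above 0.3.** The plan calls 0.3 conservative, and the Biomechanical Testing Protocol reports ICCs of 0.926 to 0.993 for knee flexion and abduction. It also gives 0.666 for the knee rotation moment, and it gives none there for hip moments, strength or balance. High reliability shrinks the effect without changing its direction.
- **Randomisation protects the trial.** It does protect the arm and interaction contrasts from this mechanism. Risk group is not randomised.

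A reader might infer that the trial would declare high-risk patients the best responders even if no arm worked. The documents do not support that. Arm effect and interaction are named in the same sentence and would both be null, and the untrained STAN arm would show the same drift. The Background question, whether HOME and STAN suffice for reduced-risk patients, is an arm contrast within risk group and is not affected.

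**Conclusion.** The point holds in a limited form. If risk group means the Aim 1 clusters, a difference between risk groups in raw change includes regression to the mean for the outcomes that also form the clusters, so it cannot be read as efficacy.

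Null rejection is about 50-60% at the plan's correlation of 0.3, 30-40% at 0.7 and 10-16% at 0.9 when three groups are forced on a continuum. It is about 5-10% where clusters are distinct enough for BIC to select them. It would be wrong to quote the 50-60% alone as the trial's error rate: it belongs to forced grouping at the lowest correlation considered. The number and correlation of measures and the cluster separation are assumptions of the simulation, not figures from the protocol.

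This mechanism does not bias the comparison of TNMT, HOME and STAN, or its interaction with risk group. The severity is should-fix, not must-fix.

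**What to change.** In Data Analysis Plan, Aim 2:

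1. Remove the stand-alone effect of risk group on change from the primary inference.
2. State that risk group means the Aim 1 cluster, if that is intended. Reconcile the equation with the text by adding risk group as an adjustment term and arm × risk group, with all subscripts defined.
3. Model the Post value on the outcome's own Pre value, arm, risk group and arm × risk group. Do not interpret the risk-group coefficient as efficacy, since baseline adjustment alone does not reliably remove the problem.
4. Base any claim about risk group and efficacy only on arm contrasts within each risk group, compared across groups.
5. Label change within a risk group as descriptive and subject to regression to the mean.

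The cost is wording in the analysis plan, with no new data or visits. The statistical price is a more limited conclusion on risk groups: the interaction has only about 62% power at 105 completers, if 0.17 is Cohen's f with three arms and three risk groups. The plan should say so.
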